#### 5.5.2.2.1 Intention to Treat Analysis (Primary Analysis)

This analysis will be performed in the ITT population. Duration of follow-up will be calculated from the date of randomization.

In addition, analyses of this secondary safety endpoint will be performed on the AT and PP populations.

#### 5.5.2.2.2 Landmark Survival Analysis

A landmark analysis for all-cause mortality will be performed, with follow-up starting at 30 days after randomization and through 12 months after randomization. This analysis will be identical to the primary analysis except that only subjects who have not been lost to follow-up, died or withdrawn by 30 days post randomization will be included and time to death or censoring will be calculated from 30 days.

#### 5.6 Analysis of Effectiveness

#### **5.6.1** Primary Effectiveness Endpoints

Treatment with the MitraClip device is expected to reduce the risk of recurrent HF hospitalization. Recurrent HF hospitalization is the primary effectiveness endpoint for the trial. Hospitalizations that are adjudicated by the CEC as related to HF using the prespecified protocol definition will be included as events in the analysis. The primary effectiveness endpoint will be analyzed from the time of randomization until the last subject completes 12 months of follow-up. All follow-up data through 24 months at the time of data cut-off will be used.

The null and alternative hypotheses are stated as:

 $H_0$ : RRR  $\leq 0$  vs.

 $H_1$ : RRR > 0

where RRR is the relative risk reduction in the rate of recurrent HF hospitalization due to treatment with the MitraClip device. The Joint Frailty Model (JFM) method will be used to model the recurrent hospitalization data and estimate the RRR.

RRR = (1- Hazard Ratio of Device vs. Control) =  $(1 - e^{\beta})$  where  $\beta$  is the regression coefficient of the recurrent HF hospitalization in the JFM model.

The primary analysis in the ITT population and other analyses are listed below. The endpoint will be met if the null hypothesis in the primary analysis is rejected at the one-sided significance level of 5%.

#### 5.6.1.1 Intention to Treat Analysis (Primary Analysis)

This analysis will be performed in the ITT population. Subjects who do not experience any HF hospitalizations and are alive will be censored on their data cut-off date. Subjects who die will be censored on the date of death. Subjects who withdraw from the study without experiencing a HF hospitalization will be censored on the date of withdrawal. Duration of follow-up will be calculated from the date of randomization. For a sensitivity analysis, duration of follow-up will also be calculated from the date of the "Treatment" visit or the randomization date if the "Treatment" visit is missing.

#### 5.6.1.2 As Treated Analysis

The analysis in the AT population will be identical to the ITT analysis with the exception that it will be performed in the AT population. Duration of follow-up will be calculated from the date of the randomization. For Subjects who undergo other intervention for HF (e.g. MV surgery, LVAD implant or heart transplant) in either group, their follow-up information after the first intervention for HF will be excluded from the AT analysis (regardless of treatment group).

For a sensitivity analysis, duration of follow-up will also be calculated from the date of the "Treatment" visit or the randomization date if the "Treatment" visit is missing.

#### 5.6.1.3 Per Protocol Analysis

The analysis in the PP population will be identical to the ITT analysis with the exception that it will be performed in the PP population. Duration of follow-up will be calculated from the date of randomization. For subjects who undergo other intervention for HF (eg. MV surgery, LVAD implant or heart transplant) in either group, their follow-up information after the first intervention for HF will be excluded from the PP analysis. For subjects in the Control group who receive the MitraClip device, their follow-up information after the MitraClip procedure will be excluded from the PP analysis (regardless of treatment group).

For a sensitivity analysis, duration of follow-up will also be calculated from the date of the "Treatment" visit.

#### 5.6.1.4 Inclusion of Unplanned Heart Failure Visits

This analysis will be identical to the ITT analysis with the exception that in addition to recurrent HF hospitalizations, Unplanned HF Visit events will be included as defined in the protocol.

An "unplanned heart failure visit" is considered to include unscheduled office visits or Emergency Department (ED) visits that meet the definition for HF hospitalization, with the exception of the 24-hour requirement.

#### **5.6.1.5** Andersen-Gill Counting Process Analysis

The Andersen-Gill (A-G) counting process method will also be used to model the recurrent hospitalization data and estimate the RRR as a sensitivity analysis.

A robust estimate of the variance will be applied in the calculation of confidence intervals and tests of hypotheses.

#### 5.6.1.6 Tipping-point Analysis

Tipping-point analysis on the primary effectiveness endpoint will be conducted as a sensitivity analysis. Subjects in the Device or Control group who withdraw from the study before completing 24-month follow-up visit will be analyzed one at a time as having experienced a HF hospitalization on the date of withdrawal.

#### 5.6.1.7 Andersen-Gill Model with a Time Varying Covariate

The A-G model assumes proportional hazards. However, it is possible that the hazard of subsequent HF hospitalization increases if the subject has experienced a prior HF hospitalization. Accordingly, the A-G model will be re-fit with a time varying indicator to account for a prior HF related hospitalization post randomization.

#### 5.6.1.8 Andersen-Gill Counting Process Analysis for Composite of Recurrent Heart-Failure Hospitalization or Death

The Andersen-Gill (A-G) counting process method will also be used to model the composite of recurrent HF hospitalization or death. The RRR and 95% confidence interval calculated from the A-G model will be provided as a sensitivity analysis. A robust estimate of the variance will be applied in the calculation of confidence intervals and tests of hypotheses.

#### 5.6.1.9 Multi-State Model

A multi-state model will be fit to the effectiveness data as a sensitivity analysis. The model will include four states corresponding to:

- State 1: "Treatment" visit
- State 2: 1st HF hospitalization
- State 3: Additional HF hospitalization
- State 4: Death

The transitions between the states will be estimated using a stratified proportional hazards regression model with a treatment group indicator (Device, Control) and with strata corresponding to the six transitions  $\{1\rightarrow 2, 1\rightarrow 4, 2\rightarrow 3, 2\rightarrow 4, 3\rightarrow 3, 3\rightarrow 4\}$ . The homogeneity of the Device effect on HF hospitalizations and death will be evaluated via a test of the treatment by strata interaction. A likelihood ratio test based on the difference between the full model (interaction) and reduced model (no interaction) likelihood ratio will be used. The estimate of the Device effect will be based on the hazard ratio of the Device vs. Control.

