#### 5 Statistical Methods

#### 5.1 Randomization and Blinding

Subjects will be randomized in a 1:1 ratio to the Device or Control groups. Randomization will be stratified by site and cardiomyopathy etiology (ischemic or non-ischemic). Randomization will be performed using permuted blocks (random block sizes) and block

sizes will not be revealed to sites. The Electronic Data Capture system will be used to randomize subjects.

The subject, some site personnel and some Sponsor personnel will be aware of treatment assignment. Sponsor statisticians will not have access to any data that combines outcomes with treatment assignment prior to performing the final analysis. No Sponsor personnel will have access to outcome data summarized by treatment until the primary endpoint analysis is complete. All events constituting primary or secondary endpoints will be adjudicated by the independent Clinical Events Committee (except embolization, which will be site reported, and MV Stenosis and SLDA, which will be assessed by the Echocardiography Core Lab), along with relationship to the MitraClip device or procedure. Every effort will be made to blind the Clinical Events Committee (CEC) to the subject's treatment assignment.

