#### 5.8.2 Primary Effectiveness Endpoint

That Require Non-elective Cardiovascular Surgery Total

At least ten thousand (10,000) simulations with converged joint frailty model were performed to calculate sample size and power for the primary effectiveness endpoint. With a fixed sample size design, 610 subjects provide approximate 80% power at the one-sided significance level of 5% for the primary effectiveness endpoint.

The following assumptions were made for the calculation of sample size:

- The enrollment rate is based on the actual monthly enrollment numbers from December 2012 to February 2016, then 20 subjects per month, thereafter
- Attrition due to withdrawals at 12 months is 7.5% in both groups
- In the EVEREST High Risk Cohort (N = 211), the lower bound of a 95% confidence interval on the HF hospitalization rate in the period pre-enrollment was ~0.6 per 12 months. The HF hospitalization rate in the Control group is therefore assumed to be 0.6 per 12 months. The HF hospitalization rate in the Device group is assumed to be 0.42 per 12 months (30% Relative Risk Reduction).
- Subjects are followed for a minimum of 12 months. All available follow-up through 24 months at the time of data cut-off will be included in the analysis.
- The mortality rate in the Control group is 27%, and in the Device group is 22%.
- To account for informative censoring of death event, a shared random effect (frailty) model for recurrent events and terminal event is used to simulate recurrent events and

death event data. The correlation between these two processes is introduced by the shared frailty distribution, Gamma distribution with mean of 1 and variance of 1. The frailty is assumed to have the same impact on the hazards for recurrent and terminal event (e.g. frailty exponent is 1). The frailty variance and frailty exponent values are estimated and determined based on the REALISM HR FMR patients data and blinded pooled COAPT roll-in and randomized data as of June, 2016. The key underlying assumptions of the JFM are

- a) The recurrent, terminating, and censoring processes all have continuous distribution so that recurrent events and death cannot happen at the exact same time.
- b) Death event precludes the observation of new recurrent HF hospitalization events, but independent censoring (e.g. withdrawal or lost-to-follow-up) does not interrupt the occurrence of recurrent HF hospitalization events.

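### The multi-state homogeneity test in SAP 5.6.1.9 spreads a one-contrast question, HF hospitalization versus death, over 5 degrees of freedom; add the 1-df contrast and report both hazard ratios

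*SAP*

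**What the plan says.** SAP 5.6.1.9 defines four states (treatment visit, first HF hospitalization, additional HF hospitalization, death). The multi-state model "will be fit to the effectiveness data as a sensitivity analysis". It is a stratified proportional hazards model with a treatment indicator, "with strata corresponding to the six transitions": 1→2, 2→3 and 3→3 end in an HF hospitalization, and 1→4, 2→4 and 3→4 end in death.

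The purpose is given as follows: "The homogeneity of the Device effect on HF hospitalizations and death will be evaluated via a test of the treatment by strata interaction". The method is: "A likelihood ratio test based on the difference between the full model (interaction) and reduced model (no interaction) likelihood ratio will be used". On estimation the section says: "The estimate of the Device effect will be based on the hazard ratio of the Device vs. Control".

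The section gives no degrees of freedom and no significance level. It does not group the three hospitalization and three death transitions, and it has no rule for what follows a significant interaction. It does not say whether the hazard ratio is pooled or transition-specific. By contrast, the treatment interaction tests in SAP 5.6.1.10 and 5.6.1.11 all state a 15% level.

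**The concern.** Whether the device acts alike on HF hospitalization and on death is one comparison of two effects. The full interaction test has as its null that six hazard ratios are equal. It therefore also tests first against later hospitalizations, and deaths from one state against deaths from another. If the real difference lies between event types, the extra degrees of freedom raise the critical value and add no signal.

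This is the only place in the SAP where the two effects are formally compared. The situation that matters is plausible. Protocol 2.2.6 expects only a modest long-term mortality reduction and asks that benefit be weighed against any raised mortality risk. If hospitalizations fall and deaths do not, the analysis should show it. A non-significant omnibus test next to one favourable hazard ratio could be read as agreement between the two.

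**Working it through.** **Degrees of freedom.** Six treatment coefficients against one common coefficient leave 6 − 1 = 5 df. These split into 2 among the three hospitalization transitions, 2 among the three death transitions, and 1 between the two event types. Only the last matches the stated purpose.

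**Inputs.** From SAP 5.8.2: 610 subjects; Control HF rate 0.6 and Device 0.42 per 12 months (hazard ratio 0.42/0.6 = 0.70); mortality 27% vs 22%; 7.5% attrition at 12 months; shared gamma frailty with mean 1, variance 1 and exponent 1; 12 to 24 months of follow-up. From SAP 5.1: 1:1 allocation. Monthly enrolment is not tabulated, so it is assumed that 370 subjects reach 24 months and 240 are uniform on 12-24 months. Constant hazards are also assumed. The test level is taken as 5%, with 15% as a variant.

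**The plan's own figure.** SAP 5.8.2 states that "610 subjects provide approximate 80% power at the one-sided significance level of 5% for the primary effectiveness endpoint". Simulating that model and fitting a joint frailty model with a one-sided 5% Wald test gave 80.2% in 2,500 runs. The set-up reproduces the plan.

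**What the planned mortality implies.** With no frailty the death hazard ratio is ln(0.78)/ln(0.73) = 0.79. With gamma frailty of variance 1 it is (1/0.78 − 1)/(1/0.73 − 1) = 0.76. Both are close to 0.70, so under planning values there is little heterogeneity to find.

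**Power by simulation.** The six-transition stratified Cox model was fitted to each simulated trial. The 5-df likelihood ratio test was compared with a 1-df test (one hospitalization and one death coefficient against one common coefficient). The HF hazard ratio is 0.70, constant within event type. Results are at the 5% level:

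| Death HR | 1 df vs 5 df, frailty variance 1 | 1 df vs 5 df, no frailty |
|---|---|---|
| Planned mortality | 7% vs 7% | 12% vs 8% |
| 1.0 | 53% vs 32% | 55% vs 32% |
| 1.2 | 86% vs 65% | 93% vs 75% |
| 1.5 | 99% vs 94% | about 99% vs 98% |

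Monte Carlo error is about 1.6 points for the first three rows (1,000 runs) and at most 2.2 for the last (500 runs). A separate set of 5,000 runs per scenario, with frailty variance 1 and 70% of subjects at 24 months, gave 55% vs 32% at death HR 1.0 and 87% vs 67% at 1.2. With both hazard ratios at 0.70 it gave rejection rates of 5.1% (1 df) and 6.8% (5 df), so the loss is in power and not from a conservative omnibus test. With only 40% at 24 months the loss stayed at about 20-23 points. A clock-reset time scale changed little.

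At a 15% level the gap is about 20 points at death HR 1.0 (73% vs 54% with frailty), 8-11 points at 1.2 (94% vs 83% with frailty, 97% vs 88% without), and 0-7 points at planned mortality.

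**Check by formula.** If effects are equal within event type, both tests share the noncentrality λ = [ln(HR_death/HR_HF)]² / (4/E_HF + 4/E_death), where E is the number of events. With frailty and death HR 1.0, the simulated trials averaged 204 + 71 + 40 = 315 hospitalizations and 149 + 51 + 28 = 228 deaths. The fitted hazard ratios were 0.75 and 1.07, because frailty shifts the marginal values. Then λ = [ln(1.07/0.75)]² / (4/315 + 4/228) = 0.1263/0.0302 = 4.18. The chi-square power at 5% is 0.50 (1 df) and 0.28 (5 df) at λ = 3.84, and 0.60 and 0.36 at λ = 4.9. The simulated 53% and 32% lie in these intervals.

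**A pooled hazard ratio.** Weighting the same log hazard ratios by events gives [315 × ln 0.75 + 228 × ln 1.07]/543 = −0.138, a pooled hazard ratio of 0.87, as simulated. With frailty variance 1 and death HR 1.0, the upper 95% limit was below 1 in about 33-35% of trials. In 24-25% this coincided with a non-significant 5-df test (52-53% without frailty). At death HR 1.2 the pooled value is about 0.93 and the coincidence 5-6% (12% without frailty). At 1.5 it is 0.2% or less.

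**The case against.** Several stronger readings are tempting, and the documents do not support them.

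A reader might infer that the test fails to address hospitalization versus death at all. That goes too far: six equal hazard ratios imply equal effects on the two event types, so the omnibus null contains the question. The stated purpose can even be read as homogeneity across all listed transitions, in which case test and purpose match.

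A reader might also infer that the plan reports only a pooled hazard ratio and so could hide harm on death. The section does not say pooled, and the interaction model it requires yields six transition-specific ratios. Any masking would come from relying on one pooled number, not from the 5 df. Mortality is assessed on its own by the Cox hazard ratio with its confidence bound and conditional superiority test (SAP 5.5.2.2), the landmark analysis (5.5.2.2.2) and Kaplan-Meier estimates (5.7.4). It also ranks first in the Finkelstein-Schoenfeld and win-ratio analyses (5.6.2.6). The multi-state analysis has no part in trial success (5.9, 5.10).

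Finally, equal effects within event type is the setting that suits the 1-df contrast best. In two simulated scenarios with added variation within event type, its lead shrank to 51% vs 38% and 50% vs 44%. For a pure first-versus-later difference the 5-df test detected 24% and the contrast 5%. This is a good reason to keep the omnibus test.

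What remains is that none of the separate mortality analyses tests whether the two effects agree. The section that does so uses a blunter test than its question needs, and it leaves the level and the reported estimates open.

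**Conclusion.** The point holds as a modest, inexpensive improvement to a non-decisional sensitivity analysis. The 5-df test does not isolate the hospitalization-versus-death contrast. It gives up roughly 20 points of power at the 5% level when the HF hazard ratio is 0.70 and the death hazard ratio is about 1.0 to 1.2.

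A reader might take 20 points as a fixed loss, but it is not. The loss is 0-4 points at the planned mortality and 2-5 points at a death hazard ratio of 1.5. At a 15% level it shrinks to 8-11 points at a death hazard ratio of 1.2.

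The roughly one-in-four chance of a favourable pooled hazard ratio beside a non-significant omnibus test applies to a null effect on death with frailty variance 1. It matters only if a pooled ratio is allowed to stand alone. All these sizes rest on the assumed accrual pattern, constant hazards, and effects equal within event type. The 5% level is also an assumption, since the section gives none.

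**What to change.** In SAP 5.6.1.9:

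- Add a 1-df likelihood ratio test as the test of the hospitalization-versus-death question. The larger model has one treatment coefficient for 1→2, 2→3 and 3→3 and one for 1→4, 2→4 and 3→4; the smaller has one common coefficient. State its significance level.
- Report the HF-hospitalization and death hazard ratios, each with a 95% CI, whatever the p-value. Do not let a pooled hazard ratio stand alone as the Device effect.
- Keep the 5-df test and the six transition-specific hazard ratios as supportive, because they can show first-versus-later or state-specific differences that the contrast misses.

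The cost is a few sentences, one extra model fit on data already collected, and one more p-value in a sensitivity analysis that does not decide trial success.

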#### 5.6.1.10 Subgroup Analyses for Primary Effectiveness Endpoint

#### **5.6.1.10.1** Sex (male vs. female)

Subgroup analyses of sex will be performed. Major baseline and clinical characteristics will be summarized by sex, and by treatment group.

The JFM model will be re-fit with the effects of treatment group, sex and the interaction of treatment group by sex. The test for the interaction effect on the primary effectiveness endpoint will be performed at the 15% level of significance.

#### 5.6.1.10.2 Etiology of Cardiomyopathy (ischemic vs. non-ischemic)

Subgroup analyses of cardiomyopathy etiology will be performed. Major baseline and clinical characteristics will be summarized by etiology of cardiomyopathy, and by treatment group.

The JFM model will be re-fit with the effects of treatment group, cardiomyopathy etiology and the interaction of treatment group by etiology. The test for the interaction effect on the primary effectiveness endpoint will be performed at the 15% level of significance.

#### 5.6.1.10.3 Left Ventricular Ejection Fraction (LVEF>40% vs. LVEF≤40%)

Subgroup analyses of Central Echocardiography Core Laboratory assessed baseline LVEF will be performed. Major baseline and clinical characteristics will be summarized by baseline LVEF and by treatment group.

The JFM model will be re-fit with the effects of treatment group, EF and the interaction of treatment group by EF. The test for the interaction effect on the primary effectiveness endpoint will be performed at the 15% level of significance.

#### **5.6.1.10.4** Extreme Surgical Risk Status

Subgroup analyses of extreme surgical risk status as assessed by the Central Eligibility Committee will be performed. Major baseline and clinical characteristics will be summarized by extreme surgical risk status, and by treatment group.

The JFM model will be re-fit with the effects of treatment group, extreme surgical risk status and the interaction of treatment group by extreme surgical risk status. The test for the interaction effect on the primary effectiveness endpoint will be performed at the 15% level of significance.

#### 5.6.1.11 Analysis of Poolability of Study Sites

Analysis of the site effect will be performed. The A-G model will include the effects of treatment received, site, and the interaction of treatment by site. The interaction test will be performed at the 15% level of significance. The study will involve up to 100 sites. It is likely that there will be wide variation in the number of subjects enrolled across sites (due to differences in site start-up times and differences in subject volumes enrolled at sites). If model convergence is not achieved, sites will be categorized into the categories described below. The model will then include the effects of treatment, site category and the interaction

of treatment by site category. In addition, a descriptive summary of recurrent HF hospitalizations will be provided by site.

• Large: Sites with more than 10 subjects

• Medium Large: Sites that enroll between 6 and 10 subjects

• Medium: Sites that enroll between 3 and 5 subjects

• Small: Sites that enroll fewer than 3 subjects.

#### 5.6.2 Secondary Effectiveness Endpoints

The secondary effectiveness endpoints will be tested at a two-sided significance level of 5%, unless otherwise specified. This primary analysis population of the secondary effectiveness endpoints will be the ITT population. Additional analyses of the secondary effectiveness endpoints will be performed on the PP and AT populations.

